4.1.9 Definition of maximum-tolerated dose

Please refer to Section 7.

4.1.10 Definition of evaluable patient

Patients that are evaluable for MTD are those who do not fulfil criteria for replacement as outlined in Section 3.3.4.4.

4.1.11 Blinding and procedures for unblinding

This Phase I trial will be handled in an open fashion by the Sponsor throughout, i.e., also for the purpose of data cleaning and preparation of the analysis. The CRF will contain information on the treatment and the dose.

4.1.12 Packaging, labelling, and re-supply

The investigational products will be provided by BI or a designated CRO. They will be packaged and labelled in accordance with the principles of Good Manufacturing Practice (GMP). Each site will be provided with an initial shipment of trial drug supply. Further medication will be automatically delivered depending on the recruitment on site using an Interactive Response Technology system.

For details of packaging and the description of the label, refer to the ISF.

4.1.13 Storage conditions

Drug supplies will be kept in their original packaging and in a secure limited access storage area according to the recommended storage conditions on the medication label. A temperature log must be maintained for documentation. If the storage conditions are found to be outside the specified range, the [REDACTED] clinical monitor (as provided in the list of contacts) must be contacted immediately.

4.1.14 Drug accountability

The Investigator, or designee, will receive the investigational drugs delivered by the Sponsor when the following requirements are fulfilled:

- Approval of the clinical trial protocol and informed consent form (ICF) by the Institutional Review Board (IRB) / ethics committee

- Availability of a signed and dated clinical trial contract between the Sponsor and the head of the investigational site
- Approval/notification of the regulatory authority (e.g., competent authority)
- Availability of the curriculum vitae of the Principal Investigator
- Availability of a signed and dated clinical trial protocol
- Availability of the proof of a medical license for the Principal Investigator
- Availability of FDA Form 1572.

Investigational drugs are not allowed to be used outside the context of this protocol. They must not be forwarded to other investigators or clinics. Patients should be instructed to return unused investigational drug.

The Investigator, or designee, must maintain records of the product's delivery to the trial site, the inventory at the site, the use by each patient, and the return to the Sponsor or alternative disposal of unused products.

These records will include dates, quantities, batch / serial numbers, expiry ('use-by') dates, and the unique code numbers assigned to the investigational product and trial patients. The Investigator, or designee, will maintain records that document adequately that the patients were provided the doses specified by the clinical trial protocol (CTP) and reconcile all investigational products received from the Sponsor. Unused or partially used drug supplies will be destroyed on site at the end of the trial (after relevant reconciliations have been completed and records reviewed by the clinical monitor).

4.2 OTHER TREATMENTS, EMERGENCY PROCEDURES, RESTRICTIONS

4.2.1 Other treatments and emergency procedures

There are no other mandatory treatments to be used in this trial or special emergency procedures to be followed. Recommendations for the management of immune-related AEs can be found in Appendix [10.2](#).

Rescue medications to reverse the actions of BI 891065 or BI 754091 are not available. Therefore, potential side effects of BI 891065 or BI 754091 have to be treated symptomatically.

Blood transfusions are allowed at any time during the trial, except to meet inclusion criteria. There must be at least 4 weeks between a patient's last transfusion and the screening laboratory assessment. Exceptions to this will be considered by the Sponsor on a case-by-case basis.

4.2.2 Restrictions

4.2.2.1 Restrictions regarding concomitant treatment

Concomitant therapy, with reasons for the treatment, must be recorded in the case report form (CRF) during the screening and treatment periods, starting at the date of signature of informed consent and ending after the residual effect period (REP). After REP, only concomitant therapy indicated for treatment of a related AE has to be reported. If a new anti-cancer treatment is started, it will be documented in the CRF, on a separate page of follow-up therapy, different from the concomitant therapies pages.

BI 891065 was found to be an inhibitor of various CYP450 enzymes *in vitro*, with K_i values in the range of 0.84 to 12 μM (see Section 1.2.1). A drug-drug interaction with other medications metabolized by these enzymes cannot be excluded. Caution should be exercised when combining BI 891065 with substrate drugs of CYP450 enzymes (1A2, 2C8, 2C9, 2C19, 2D6, 3A4). Table 4.2.2.1:1 provides a list of restricted and permitted medications. Alternatives with less potential for CYP450 based interactions should be considered, where available. Close monitoring for potential adverse reactions is warranted and patients should be informed about potential signs and symptoms of such adverse reactions (e.g., muscle pain). BI 891065 was also found to be an inhibitor of the drug transporters P-glycoprotein and BCRP *in vitro*, with IC_{50} values of 0.034 μM and 0.18-0.59 μM , respectively (see Section 1.2.1). Caution should be exercised when combining BI 891065 with P-gp and BCRP substrates. Table 4.2.2.1:1 provides a list of restricted and permitted medications.

Table 4.2.2.1:1 Restricted medication when coadministered with BI 891065

Sensitive CYP1A2, CYP2C8, CYP2C9 and CYP2C19, CYP2D6, CYP3A4 substrates with a high probability of exposure increase in combination with BI891065	Permitted if strictly indicated and with judicious dosing	Buspirone, Lovastatin, Simvastatin and Nisoldipine
Sensitive CYP1A2, CYP2C8, CYP2C9 and CYP2C19, CYP2D6, CYP3A4 substrates with a medium probability of exposure increase in combination with BI891065	Permitted if strictly indicated and with judicious dosing	Atorvastatin, Tacrolimus, Cisapride, Terfenadine, Midazolam, Saquinavir, Rifabutin, and Sertraline
Sensitive CYP1A2, CYP2C8, CYP2C9 and CYP2C19, CYP2D6, CYP3A4 substrates with a low probability of exposure increase in combination with BI891065	Permitted if strictly indicated and with judicious dosing	Alfentanil, Amodiaquine, Felodipine, Loperamide, Maraviroc, Methadone, Montelukast, Nifedipine, Nimodipine, Pioglitazone, Repaglinide, Trazodone, Triazolam, Verapamil and Zolpidem.
Pgp substrates (partly with narrow therapeutic margin)	Not Permitted	Dabigatran etexilate Digoxin
Pgp substrates and in addition involvement of CYP3A4 with narrow therapeutic margin	Permitted if strictly indicated and with judicious dosing	Apixaban Rivaroxaban
Pgp and BCRP substrates with a probability of exposure increase in combination with BI891065	Permitted if strictly indicated and with judicious dosing	Fexofenadine, Verapamil and Rosuvastatin
Immunosuppressive medications* at doses exceeding 10 mg/day; TNF α blockers	Not Permitted*	Prednisone or equivalent, Methotrexate, Azathioprine
Live attenuated vaccines	Not Permitted during the trial through 30 days after the last dose of investigational product	
Herbal preparations/medications	Not Permitted from 7 days prior to first dose of study treatment	St. John's wort, Kava, Ephedra (ma huang), Gingko biloba, Dehydroepiandrosterone (DHEA), Yohimbe, Saw palmetto, and Ginseng

*The following caveat applies for immunosuppressive medications:

- Use of immunosuppressive medications for the management of investigational product-related AEs or in patients with contrast allergies is acceptable, and does not necessarily warrant immediate treatment discontinuation. In addition, use of inhaled, topical, intranasal corticosteroids or local steroid injections (e.g., intra-articular injection) is permitted. Temporary uses of corticosteroids for concurrent illnesses (e.g., food allergies, computed tomography [CT] scan contrast hypersensitivity) are acceptable upon discussion with the [REDACTED] Medical Monitor.
- For the treatment of CRS, supportive therapy including steroids and / or interleukin 6 receptor (IL6R) antagonists (R15-0031) may be used as clinically indicated.

4.2.2.2 Restrictions on diet and life style

Patients should be instructed to avoid exposure to direct sunlight (including sunlamps), to use a sunblock (minimum sun-protection factor 30), and to wear clothing and sunglasses that protect against sun exposure during treatment and for 4 weeks after the last administration of BI 891065.

The usual restrictions on diet and life style that were already applicable for a given patient before entry into the trial, according to his/her medical condition, have to be continued, if feasible with the following caveats:

- Fasting requirements on PK days are described in Section 4.1.5.1
- Part B patients will be asked to eat a specific meal per Section 6.2.2.1.

4.2.2.3 Contraception requirements

Women of childbearing potential and men able to father a child must use the contraception methods described in the patient information.

4.3 TREATMENT COMPLIANCE

The investigational products should only be used as directed in this protocol. For BI 754091 administration days, BI 891065 will be administered orally approximately 30 minutes after the end of the infusion of BI 754091, and only if considered safe by the Investigator.

4.3.1 BI 891065

Patients are requested to bring all remaining BI 891065 including empty package material with them when attending visits. Details of treatment with investigational product for each patient will be recorded in the eCRF.

The trial personnel at the investigational site will account for all drugs dispensed and for appropriate destruction. Certificates of delivery and destruction should be signed.

Based on counts, treatment compliance will be calculated as shown in the formula below. Compliance will be verified by the CRA authorised by the Sponsor.

$$\text{Treatment compliance (\%)} = \frac{\text{Number of tablets actually taken} \times 100}{\text{Number of tablets that should have been taken}}$$

If the number of doses taken is not between 80% to 100%, site staff will explain to the patient the importance of treatment compliance. Different tablet strengths need to be taken into consideration for computation.

4.3.2 BI 754091

BI 754091 will be administered by i.v. infusion at the sites by the Investigator and/or trained site personnel, and dosing will be recorded in the eCRF. Therefore, actual dosing is expected to precisely follow the dose, as determined from the previous monotherapy study (Trial BI 1381.1). Missed or interrupted doses will be recorded in the eCRF with the associated reasons. The method of collecting dosing information assures that total exposure can be calculated programmatically taking into account any missing doses.

5. ASSESSMENTS

5.1 ASSESSMENT OF EFFICACY

5.1.1 NSCLC tumour assessment and solid tumour assessment

Tumour response will be evaluated at the site according to RECIST Version 1.1 (R09-0262) and/or iRECIST (R17-0923 and Appendix 10.6). The assessment by the Investigator and/or the local radiologist will be the basis for continuation or discontinuation of the trial in an individual patient (in addition to safety). Duplicates of the images will be collected and stored by a BI-appointed representative, and may be used for future independent central RECIST/iRECIST review, if deemed appropriate. In addition, the images may be used for further analysis to explore the potential for enhanced and improved baseline and on-treatment markers/patterns of early efficacy based on comprehensive quantitative CT metrics (i.e., radiomics features, assessed in standard-of-care medical imaging data).

The patients will be re-evaluated every 6 weeks for the first 6 months and then every 9 weeks thereafter until the earliest of PD, death, or last evaluable tumour assessment before start of subsequent anti-cancer therapy or until the end of the trial. The baseline scan(s) (CT scan and/or MRI according to Investigator's decision) from screening must have been performed within 4 weeks prior to treatment with the trial drug(s) and the Investigator will record the target (5 target lesions in total and maximum 2 per organ) and non-target lesions at baseline in the patient's medical records and in the CRF before the start of treatment. The same method of assessment and the same technique must be used to characterise each reported lesion at baseline and during treatment. Lesions in previously irradiated areas may not be considered measurable at baseline unless the lesions occurred after irradiation. Tumour assessment will be performed at screening (as close as possible to the treatment start and no

more than 28 days before the start of trial treatment), every 6 weeks for the first 6 months and every 9 weeks thereafter, and at the EOT visit (if not performed within the last 4 weeks).

If the patient stops with the trial medication for a reason other than progression, the tumour assessment according to RECIST v1.1 and iRECIST will be performed according to standard of care until the last follow-up needed according to the protocol (progression, death, lost to follow-up, end of the trial). Patients will be allowed to stay on treatment in the case of initial radiological PD, if the Investigator feels that it is in the patient's best interest, the patient signs an informed consent form specific for this circumstance, and the criteria listed in Section 3.3.4.1 are met.

5.2 ASSESSMENT OF SAFETY

5.2.1 Physical examination

A complete physical examination will be performed at the time points specified in [Part A Flow Chart](#), [Part B Flow Chart](#), and [Part C Lung Flow Chart](#). It includes at a minimum general appearance, neck, lungs, cardiovascular system, abdomen, extremities, and skin. Motoric functionality will be examined with an additional focus on the function of the cranial nerve VII. Any signs of facial nerve palsy have to be monitored closely until resolution.

Measurement of height and body weight will be performed at the time points specified in [Part A Flow Chart](#), [Part B Flow Chart](#), and [Part C Lung Flow Chart](#).

During the physical examination, the patient should be assessed for possible adverse events. The results must be included in the source documents available at the site.

5.2.2 Vital signs

Vital signs will be evaluated at the time points specified in [Part A Flow Chart](#), [Part B Flow Chart](#), and [Part C Lung Flow Chart](#) prior to blood sampling and trial treatment administration. This includes body temperature, systolic and diastolic blood pressure and pulse rate (electronically or by palpation count for 1 minute). All except body temperature need to be taken in a seated position after 5 minutes of rest. Oxygen saturation will be measured, if needed.

Blood pressure and heart rate may also be measured after infusion of BI 754091 or at any time that the Investigator deems it is necessary.

5.2.3 Safety laboratory parameters

For the sampling time points please see [Part A Flow Chart](#), [Part B Flow Chart](#), and [Part C Lung Flow Chart](#) for each part. All analyses will be performed locally. Patients do not have to be fasted for the blood sampling for the safety laboratory tests.

Instructions regarding sample collection, sample handling/ processing and sample shipping are provided in the Laboratory Manual in the ISF.

Clinically relevant abnormal findings as judged by the Investigator will be reported as adverse events (please refer to Section 5.2.6).

In case the criteria for hepatic injury are fulfilled, a number of additional measures will be performed (please see Section 5.2.6.4.5 and the Potential DILI Checklist provided in the ISF). The amount of blood taken from the patient concerned will be increased due to this additional sampling.

Safety laboratory tests will include the following parameters:

Haematology

The standard haematology panel will consist of: haemoglobin, red blood cell count, haematocrit, mean corpuscular volume, white blood cell count, differential blood count (preferably expressed in absolute values), platelets, haptoglobin and reticulocytes.

Biochemistry

The standard biochemistry panel will consist of glucose, sodium, potassium, chloride, calcium, phosphate, venous bicarbonate HCO₃, creatinine, AST, ALT, alkaline phosphatase, lactate dehydrogenase, total, direct and indirect bilirubin, total protein, albumin, urea nitrogen (or urea in lieu of urea nitrogen), uric acid and creatinine kinase (CK). If CK is elevated, then CK-MB [cardiac], Troponin I/Troponin T, and myoglobin should be reactively tested.

A thyroid panel (TSH, free T4, and free T3) will be done during Parts B and C at the time of each standard biochemistry panel.

If symptoms of pancreatitis are observed, amylase and lipase should be tested at the discretion of the Investigator.

Coagulation

Activated partial thromboplastin time (aPTT) and prothrombin time (PT) (expressed either in seconds or as percentage) will be tested according to the timing in [Part A Flow Chart](#), [Part B Flow Chart](#), and [Part C Lung Flow Chart](#).

Urine

Urine (pH, glucose, erythrocytes, leukocytes, protein, and nitrite) will be analysed by dipstick (semi-quantitative measurements).

Pregnancy test

A beta human chorionic gonadotropin (β -HCG) pregnancy test in serum will be performed for women of childbearing potential at screening. Thereafter, this test may be done in serum or urine on Day 1 of each cycle, at the EOT visit, and at the 30-day safety follow-up visit.

Virology

At screening, tests according to local standards for HIV infection and hepatitis B (and if positive, anti-HBs, anti-HBc antibodies, and HBV DNA) and hepatitis C should not be older than 28 days.

Alpha-1 acid glycoprotein

One plasma sample will be taken for alpha-1 acid glycoprotein (AGP) analysis at the beginning of Cycles 1 and 2 at the time of the safety laboratory tests (prior to BI 891065 administration).

If laboratory safety investigations have been performed >72 hours prior to the first trial treatment, the results of the new safety laboratory investigations performed within 72 hours of first treatment must be available to reconfirm eligibility.

5.2.4 Electrocardiogram

Standard 12-lead (I, II, III, aVR, aVL, aVF, V1 - V6) resting electrocardiograms (ECGs) will be digitally recorded at various time points throughout the trial. The [Part A Flow Chart](#), [Part B Flow Chart](#), and [Part C Lung Flow Chart](#) outline which visits will require ECGs, and [Appendix 10.3](#) outlines which time points require triplicate ECGs to be done along with certain PK samples.

All ECGs will be obtained after the patient has been resting supine for at least 10 minutes prior to the indicated times. All ECGs should be recorded with the patient in the same physical position.

Electrocardiogram machines will be provided to facilitate central readings. Before study start, the study sites will be trained for the proper use of the equipment and transfer of the electronic data to the vendor. While all ECGs will be transmitted to the central vendor, only the baseline, 6-hour, 8-hour, and 24-hour readings will be reviewed directly. The other readings would be analyzed only if the PK analysis points to a t_{max} deviating from the predicted t_{max} .

ECGs may be repeated for quality reasons and the repeated recording used for analysis. If necessary, additional ECGs may be recorded for safety reasons. In Part C, triplicate readings are required with pharmacokinetic sample collection as indicated in [Table 10.3: 3](#). When triplicate ECGs are not done, single readings will be done for safety purposes as indicated in [Part C Lung Flow Chart](#).

The ECG recordings must also be analysed and checked for abnormality by the Investigator (or designated physician) who will also calculate the QTcF value for each time point as the mean of the 3 ECGs. Particular attention must be paid to T wave inversions. It is not mandatory to wait for central evaluation of ECGs to make clinical decisions. Clinically relevant abnormal findings will be reported either as baseline condition (if identified at the screening visit) or otherwise as adverse events and will be followed up and/or treated as

medically appropriate. CTCAE Version 5.0 will be used for the grading of prolonged QTcF intervals.

In case of related ECG changes and whenever the Investigator deems necessary, additional ECG monitoring will be performed in the respective and later courses of treatment. The ECGs will be recorded using dedicated equipment provided by a vendor. The ECGs will be sent for evaluation by a central vendor. Data from this central review will be taken for retrospective data analysis. To allow for a heart rate correction of QT intervals the QT intervals will be matched to the preceding RR intervals using at least QTcF (Fridericia's formula $QTcF = QT/RR^{-1/3}$) and QTcB (Bazett's formula $QTcB = QT/RR^{-1/2}$).

In case of QTcF prolongation to >500 ms (mean of 3 ECGs) AFTER receiving therapy, the Investigator will initiate further ECG monitoring and diagnostics (e.g., check electrolytes and check concomitant therapy that may be contributing to QTcF prolongation) and if required provide adequate treatment according to medical standards. The patient will be discharged from the investigational site only after resolution of ECG findings as assessed by the Investigator.

In case of occurrence of symptoms suggestive of arrhythmia related to QTcF prolongation, a cardiologic evaluation will be performed, and treatment will be provided according to medical standards at the discretion of the Investigator.

In order not to confuse an ECG recording, PK samples should be taken after performing the ECG.

The centralised ECG evaluation will include the semi-automatic determination of the RR, PR interval, QRS complexes, and QT intervals.

All interval measurements in one patient will be performed on the same lead. The intervals will be measured from four cardiac cycles (beats) in lead II. If lead II shows a flat T wave or is not measurable for any reason, lead V5 will be used, or if that lead is not measurable, then lead I will be used.

Central morphological analyses of the ECGs (cardiologic assessments) will be performed by a board-certified cardiologist or equivalent. The cardiologist will interpret one ECG per time point. In case of triplicate ECG recordings per time point, this ECG will be selected randomly. In case additional (unscheduled) ECGs due to safety reasons are recorded at the study site, all ECGs of this time point including the additional ECGs will undergo interpretation. The ECG interpretation will include an overall assessment (normal, abnormal, not assessable) as well as assessments concerning rhythm, conduction, presence of myocardial infarction, ST segment deviations, T wave morphology, and U wave morphology findings.

Abnormalities detected during centralised ECG evaluation will not necessarily qualify as AEs. In case of clinically relevant abnormalities (e.g., heart blocks or large changes in interval duration) the ECG core laboratory may contact the Investigator and vice versa.

Centrally assessed ECGs will comply with the ICH E14 guidance document and supplements (R05-2311, R13-0801, R13-4095) as well as the FDA requirements for annotated digital ECGs (R09-4830).

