3.3.3 Exclusion criteria

1. Major surgery (major according to the Investigator's and/or Medical Monitor's assessment) performed within 12 weeks prior to randomization or planned within 12 months after screening (e.g., hip replacement)
2. Presence of other active invasive cancers other than the one treated in this trial within 5 years prior to screening, except appropriately treated basal cell carcinoma of the skin, or *in situ* carcinoma of uterine cervix, or other local tumours considered cured by local treatment
3. Patients who must or wish to continue the intake of restricted medications (see Section 4.2.2.1) or any drug considered likely to interfere with the safe conduct of the trial
4. Previous administration of BI 891065 or BI 754091
5. Currently enrolled in another investigational device or drug trial, or less than 30 days since ending another investigational device or drug trial(s), or receiving other investigational treatments.

¹ A woman is considered of childbearing potential (WOCBP), i.e. fertile, following menarche and until becoming postmenopausal unless permanently sterile.

Permanent sterilisation methods include hysterectomy, bilateral salpingectomy and bilateral oophorectomy. Tubal ligation is NOT a method of permanent sterilisation.

A postmenopausal state is defined as no menses for 12 months without an alternative medical cause.

6. Patients who have been treated with any other anticancer drug within 4 weeks or within 5 half-life periods (whichever come earlier) prior to first administration of BI 891065. At least 7 days must have elapsed between the last dose of such agent and the first dose of study drug.
7. Persistent toxicity from previous treatments that has not resolved to \leq Grade 1 (except for alopecia and Grade 2 neuropathy due to prior platinum-based therapy)
8. Active, known or suspected autoimmune disease except vitiligo or resolved asthma/atopy
9. Interstitial lung disease
10. Any of the following cardiac criteria:
 - Mean resting corrected QT interval (QTcF) >470 msec
 - Any clinically important abnormalities (as assessed by the investigator) in rhythm, conduction, or morphology of resting ECGs, e.g., complete left bundle branch block, third degree heart block

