7.8.4 ECG

For all 3 trial parts, analyses of ECG will be descriptive in nature. Newly emergent abnormalities will be recorded and analysed as adverse events.

In addition, statistical ECG analyses will be performed for the centrally evaluated digital ECG recordings as follows.

Derivation of ECG variables

Three replicate digital ECG recordings will be collected as specified in the flowchart of the CTP. Each of the three recorded single ECGs will then be evaluated semi-automatically for cardiac intervals, which comprise the RR, PR and QT interval and the QRS complex. Measurements of these intervals will be made on four (possibly consecutive) cardiac cycles from the lead chosen (usually lead II). The measurements of the cardiac cycles will be stored in the database, i.e. usually 12 values per time point. The four cardiac cycles will be averaged prior to the calculation of the heart rate and heart rate corrected QT intervals (QTc).

The heart rate will be derived from the RR interval as

$$\text{HR [beats/min]} = 60000/\text{RR [ms]}$$

Heart rate corrected QT intervals (generally denoted by QTc) will be calculated using Fridericia's (QTcF) formula and Bazett's formula (QTcB):

- $\text{QTcF [ms]} = (1000/\text{RR})^{(1/3)} * \text{QT [ms]}$
- $\text{QTcB [ms]} = (1000/\text{RR})^{(1/2)} * \text{QT [ms]}$

Further aggregation of the three replicate ECG intervals and HR at each scheduled time point will then be performed using arithmetic means. Additional averaging over 1-3 time points will be performed to derive the baseline values: they will be calculated as the mean values of the 1-3 triplicate ECG recordings collected pre-dose on Day 1. These mean values will be used for the derivation of the ECG variables as they are specified in [Section 5.4.3](#).

[figure not shown]
ECG analyses

[figure not shown]
For all ECG variables, listings of individual data will be shown in the appendix of the CTR. Absolute values and changes from baseline in QTcB interval as well as the percentage changes for PR interval and QRS complex will only be displayed in listings.

Absolute values and changes from baseline in QTcF interval, QT interval, HR, PR interval, and QRS complex will be summarised descriptively by treatment, cycle, day, and time point using the ECG set. The time profiles of mean and standard deviation for the absolute values and changes from baseline on treatment will be displayed graphically by treatment.

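### The QTcF and QTcB formulas in protocol Section 5.2.4 have inverted exponents and contradict the SAP; applied literally, they could misclassify some patients against the 470 ms and 500 ms limits

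*Protocol*

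**What the plan says.** Protocol Section 5.2.4 gives the two heart-rate corrections as "formula $QTcF = QT/RR^{-1/3" and "formula $QTcB = QT/RR^{-1/2" (both in the markup in which the PDF text was read, cut before the closing bracket). No unit for RR is stated. The formulas follow directly after the sentences on the central vendor's evaluation and its use for retrospective analysis.

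The same section gives the site a role. The investigator or a designated physician checks the recordings, "who will also calculate the QTcF value for each time point as the mean of the 3 ECGs", and may act clinically before the central evaluation is available. Two limits use QTcF without restating a formula:

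- Exclusion criterion 10 in Section 3.3.3: "Mean resting corrected QT interval (QTcF) >470 msec".
- The on-treatment rule in Section 5.2.4: "In case of QTcF prolongation to >500 ms (mean of 3 ECGs) AFTER receiving therapy".

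SAP Section 7.8.4 says that the corrected intervals "will be calculated using Fridericia's (QTcF) formula and Bazett's formula (QTcB") and gives "QTcF [ms]} = (1000/\text{RR})^{(1/3)} * \text{QT [ms", with RR in milliseconds and the analogous square-root form for QTcB.

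**The concern.** The two governing documents give opposite corrections for the same safety variable. The SAP form raises QTc above QT at fast heart rates and lowers it at slow ones. The protocol form, read literally, does the reverse, so above 60 bpm it understates QTcF.

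This is more than a clerical matter, for three reasons. The protocol offers no other QTcF formula. It asks the site to calculate QTcF and does not require the site to wait for the central reading. An entry exclusion and an on-treatment trigger in a first-in-human trial depend on the value, as does the CTCAE grading of QTcF prolongation in the same section.

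At stake is whether a site value worked out from the printed expression could admit a patient whom the exclusion was meant to keep out, turn away an eligible one, or miss or falsely raise the on-treatment trigger. Such site values would also disagree with the central values in the report.

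**Working it through.** The plan states no worked QTcF value, so there is no figure to reproduce. The check compares the two formulas.

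**Inputs**

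- Protocol 5.2.4: QTcF = QT / RR^(-1/3).
- SAP 7.8.4: QTcF = (1000/RR)^(1/3) × QT with RR in ms, and HR = 60000/RR.
- Limits: >470 ms (protocol 3.3.3) and >500 ms (protocol 5.2.4).
- Assumptions: RR in seconds for the protocol formula, RR = 60/HR; the QT and heart-rate pairs are illustrative.

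**Step 1: direction.** QT / RR^(-1/3) = QT × RR^(1/3). With RR in seconds the SAP form is QT / RR^(1/3). The ratio of printed to SAP value is therefore RR^(1/3) × RR^(1/3) = RR^(2/3). For QTcB the same argument gives QT × RR^(1/2) against QT / RR^(1/2), a ratio of RR.

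**Step 2: size of the discrepancy in QTcF.**

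| HR (bpm) | RR (s) | Ratio RR^(2/3) | QT 400 ms: SAP | QT 400 ms: printed |
|---|---|---|---|---|
| 50 | 1.200 | 1.129 | 376.4 | 425.1 |
| 60 | 1.000 | 1.000 | 400.0 | 400.0 |
| 75 | 0.800 | 0.862 | 430.9 | 371.3 |
| 90 | 0.667 | 0.763 | 457.9 | 349.4 |
| 100 | 0.600 | 0.711 | 474.3 | 337.4 |

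The values agree only at 60 bpm.

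**Step 3: when a decision changes.** The printed value reads 470 ms when the SAP value is 470 / RR^(2/3), and 500 ms when it is 500 / RR^(2/3). Decisions differ only for SAP values between the limit and that point:

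| HR (bpm) | 470 ms exclusion: SAP values misclassified | 500 ms trigger: SAP values misclassified |
|---|---|---|
| 50 | 416.2 to 470 (false exclusion) | 442.8 to 500 (false trigger) |
| 75 | 470 to 545.4 (missed) | 500 to 580.2 (missed) |
| 90 | 470 to 615.9 (missed) | 500 to 655.2 (missed) |

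Outside these bands both formulas lead to the same decision.

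**Step 4: examples.**

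| QT (ms), HR (bpm) | SAP QTcF | Printed QTcF | Effect |
|---|---|---|---|
| 420, 90 | 480.8 | 366.9 | exclusion missed |
| 440, 90 | 503.7 | 384.4 | exclusion and trigger missed |
| 450, 50 | 423.5 | 478.2 | false exclusion |
| 480, 50 | 451.7 | 510.1 | false exclusion and false trigger |
| 400, 75 | 430.9 | 371.3 | none |
| 380, 70 | 400.0 | 361.0 | none |

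**Step 5: the unit.** If RR is entered in milliseconds, QT 400 ms at 80 bpm (RR = 750 ms) gives 400 × 750^(1/3) ≈ 3,634 ms. That is plainly impossible and would be noticed. A silent error needs RR in seconds.

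**The case against.** The strongest reply is that nobody need have used the printed expression. It sits in the text on central evaluation, and SAP 7.8.4, which governs that analysis, has the correction the right way round. The protocol names Fridericia's method, so a site could apply it without relying on the exponent. Sites are supplied with ECG machines and trained on them, and the documents do not say whether those machines report QTcF. The instruction to calculate QTcF as a mean of three ECGs can be read as averaging three values already corrected. Exclusion criterion 10 cites no formula. The vendor directly reviews the baseline, 6-, 8- and 24-hour readings, and the core laboratory may contact the investigator about large interval changes. Finally, the formula was read from a PDF by a program; a multiplication sign read as a slash would make both expressions correct.

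Most of this stands, and it limits the point to what could happen under literal use. It does not remove the contradiction. The same inversion appears in both formulas, which makes a reading error less likely but does not exclude it, so the PDF should be checked first. Central review is also only a partial safeguard: Section 5.2.4 has only the listed readings reviewed directly, and SAP Section 4 reports that tmax appears earlier than expected. At earlier post-dose times the site's value may have been the only prompt one.

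**Conclusion.** The formulas as printed are inverted for both QTcF and QTcB and contradict the SAP. With RR in seconds, the printed QTcF is too low above 60 bpm and too high below it, by the factor RR^(2/3): 0.76 at 90 bpm, 0.86 at 75 and 1.13 at 50. A site applying the expression literally could misclassify patients within the bands shown above.

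A reader might infer three stronger conclusions, none of which the documents support:

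- That both limits give wrong answers at every heart rate other than 60 bpm. The QTcF value differs at every such rate, but a decision changes only when the two values straddle 470 or 500 ms.
- That ineligible patients were enrolled or on-treatment prolongation was missed. Nothing shows which formula the sites or the vendor's machines used.
- That the trial's ECG results are wrong. The planned analysis of centrally evaluated recordings uses the SAP formula.

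The conclusion rests on the printed signs being confirmed in the source PDF and, for the magnitudes, on RR being in seconds.

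**What to change.** After checking the source PDF:

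1. Correct Section 5.2.4 to QTcF = QT/RR^(1/3) and QTcB = QT/RR^(1/2), with RR stated to be in seconds. This is identical to SAP 7.8.4.
2. State that the protocol's QTcF limits use this formula.
3. Send sites a short clarification.

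The limits and the clinical rules attached to them are not in question and stay unchanged.

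Optionally, list patients whose centrally read baseline QTcF exceeds 470 ms, and report any under the existing important-deviation code A1 in SAP Section 6.2, which already covers exclusion criterion 10. The SAP's QTc categories cut at 450, 480 and 500 ms (Section 5.4.3), so they would not isolate these patients. The SAP baseline is the Day 1 pre-dose mean, which may differ from the screening ECG, so a hit calls for a look at the screening record and is not in itself proof of an entry violation.

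The cost is two exponents and a unit in a protocol amendment, one letter, and, if wanted, one programmed check on ECG data already collected.
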